2.5.4 Windows for time points

Data analyzed by time point (including efficacy, laboratory safety data, vital signs, ADA) will be summarized using the analysis windows given in Table 5, Table 6 and Table 7. These analysis windows will be applicable for all analyses, and they are defined to provide more homogeneous data for time point-specific analyses.

Time point	Targeted study day	Analysis window in study days
	Targeted Study day	Analysis window in study days
Week 8	57	43 to 70
Week 12	85	71 to minimum (98; study day corresponding to the first
		injection with IMP from kit allocated at Week 12 re-supply
		IVRS contact)
Week 24	169	155 to 182ª

Property of the Sanofi Group - strictly confidential

19-Feb-2021		
Version	number:	2

Time point	Targeted study day	Analysis window in study days	
------------	--------------------	-------------------------------	--

Study days are calculated from the day of first double-blind IMP injection, the day of first double-blind IMP injection being Day 1. For randomized but not treated patients, Day 1 is the day of randomization.

^a 155 to 182 for patients not entering the OL period or minimum of 182 or study day corresponding to the first OL injection for patients entering the open-label extension

Time point	Targeted study day	Analysis window in study days
Week 32	57	36 to 77
Week 44	141	120 to 161
Week 56	225	204 to 245
Week 68	309	288 to 329
Week 80	393	372 to 413
Week 92	477	456 to 497
Week 104	561	540 to 581

Table 6 - Analysis windows definition for OL period

Study days are calculated from the day of first OL IMP injection, the day of first OL IMP injection being Day 1.

If multiple valid values of a variable exist within an analysis window, the value collected at the scheduled visit will be used if within the analysis window. Otherwise the nearest from the targeted study day or time will be selected. If the difference is a tie, the value after the targeted study day or time will be used

For all endpoints except PK, if multiple valid values of a variable exist within a same day, then the first value of the day will be selected when time is available, else the scheduled visit will be selected.

PK Concentration will be analyzed following time windows as defined below in Table 7. If the date of the previous injection is unknown, the alirocumab concentration will not be considered for the analysis.

PK variables	Time window (D1 = day of previous injection or day of last injection $C_{follow-up}$)	
	Q2W regimen	Q4W regimen
Ctrough	Day 9 to Day 22	Day 23 to Day 36

Table 7 Time windows for PK variables definition

If multiple valid values satisfy the C_{trough} criteria, the nearest from the targeted study day (ie, Day 15/32 for $C_{through}$, Day 1 being the day of previous injection) will be selected. If the difference is a tie, the value after the targeted study day will be used.

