2.1.7 Pharmacokinetic variables

Concentrations of total alirocumab, total and free PCSK9 in serum are assessed during the doubleblind period at Visit 4 (Week 0/Day 1), Visit 5 (Week 8), Visit 6 (Week 12) and Visit 7 (Week 24).

Pharmacokinetic variable is the total alirocumab concentration at each time point. Depending on the timing of the sample versus the previous injection, C_{trough}, will be defined as follows:

- C_{trough} for Q2W regimen: alirocumab concentration sample taken between 8 and 21 days after previous injection of alirocumab (ie, just prior the next injection).
- C_{trough} for Q4W regimen: alirocumab concentration sample taken between 22 and 35 days after previous injection of alirocumab (ie, just prior the next injection).

Total alirocumab concentration and total and free PCSK9 concentration will be described following time windows as defined in Section 2.5.4 in Table 7.

Of note, for patients with a dose adjustment from Q4W dosing regimen to Q2W dosing regimen, the C_{trough} will be defined according to the regimen received at the time of the sample collection.

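### The Q4W trough target in SAP 2.5.4 should be Day 29, not Day 32, and Table 7 should count days from the previous alirocumab injection, as SAP 2.1.7 does

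*SAP*

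**What the plan says.** SAP 2.1.7 defines the Q4W trough as an "alirocumab concentration sample taken between 22 and 35 days after previous injection of alirocumab". The Q2W trough is defined in the same way at 8 to 21 days. The section sends the reader to Table 7 in SAP 2.5.4 for the windows. It adds that patients adjusted from Q4W to Q2W are classed by the regimen in use when the sample is taken.

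Table 7 gives the Q4W window as "Day 23 to Day 36" and the Q2W window as Days 9 to 22. Its header sets the origin as "D1 = day of previous injection or day of last injection", without naming the product.

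The text below the table begins "If multiple valid values satisfy the" trough criteria. It then takes "the nearest from the targeted study day (ie, Day 15/32 for" the trough, Q2W first and Q4W second, with Day 1 again the day of the previous injection. It ends: "If the difference is a tie, the value after the targeted study day will be used".

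**The concern.** There are two separate points.

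First, the two target days do not follow one rule. Day 15 is the day on which the next Q2W injection falls due. Day 32 is 3 days after the next Q4W injection falls due. A target that is too late can pass over a sample taken on time in favour of a later one, and only in the Q4W cohort.

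Second, the origin of the day count differs between the two SAP sections, and the difference has consequences in the Q4W cohort. From Week 12, alirocumab patients who are not dose-adjusted alternate alirocumab with placebo to keep the blind (Protocol 8.1). IMP includes placebo (Protocol 8.1), and the dosing date recorded with each PK sample is that of the last IMP administration (Protocol 9.3.1.1). A programmer who takes Table 7 and that recorded date at face value would count from a placebo injection. At stake are the Q4W trough and PCSK9 summaries in SAP 2.4.8.

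**Working it through.** **Inputs**
- Targets Day 15 / Day 32, with ties going to the later value: SAP 2.5.4.
- Windows Days 9 to 22 and Days 23 to 36: SAP Table 7.
- Dosing intervals of 14 and 28 days, injections within ±3 days: SAP 2.4.3.2.
- Post-dose PK samples at Weeks 8, 12 and 24: SAP 2.1.7. They are taken before injection: Protocol 10. The Week 24 visit is ±3 days: Protocol 10.1.3.4.
- Injections after Week 12 in non-adjusted Q4W alirocumab patients: alirocumab at Weeks 12, 16 and 20, placebo at Weeks 14, 18 and 22. These weeks are inferred from the alternating schedule; the documents do not tabulate them.

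**Step 1: reproduce the targets.** With Day 1 as the injection day, target = interval + 1.
- Q2W: 14 + 1 = Day 15. This matches the SAP.
- Q4W: 28 + 1 = Day 29. The SAP has Day 32, which is 31 days after injection.

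Other rules do not rescue the pair:
- interval alone: 14 / 28;
- window midpoint: (9 + 22)/2 = 15.5 and (23 + 36)/2 = 29.5;
- interval + 3 + 1: 18 / 32;
- interval − 3 + 1: 12 / 26.

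None gives both 15 and 32. Position in the window points the same way. Day 15 is 6 days from the start and 7 from the end of its window, and Day 29 is also 6 and 7. Day 32 is 9 and 4.

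**Step 2: effect on selection.** Take two valid samples on days a < b. With target 29 and ties going to the later value, the earlier sample is chosen when a + b ≥ 59. With target 32, the later sample is chosen when a + b ≤ 64. The two targets therefore disagree when a + b is 59 to 64. Days 23 to 36 contain 14 × 13/2 = 91 pairs. The counts for sums 59, 60, 61, 62, 63 and 64 are 7 + 6 + 6 + 5 + 5 + 4 = 33 pairs. In all 33, target 32 takes the later sample, by 1 day (30 and 31) to 13 days (23 and 36). For a sample on Day 29, a second sample on any of Days 30 to 35 displaces it (Day 35 by the tie rule). One on Day 36 does not.

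These are possible pairs, not expected frequencies. With one valid sample the target is never used. The nominal Week 8 and Week 12 samples both fall on Day 29 and are kept under either target.

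**Step 3: origin of the day count at Week 24.** Study day = 7 × week + 1, so Weeks 20, 22 and 24 are Days 141, 155 and 169.
- From alirocumab at Week 20: 169 − 141 + 1 = Day 29. With ±3 days on both injection and visit, the range is Days 23 to 35, always inside Days 23 to 36.
- From placebo at Week 22: 169 − 155 + 1 = Day 15. The range is Days 9 to 21, never inside Days 23 to 36.

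The limits themselves agree across the two sections: 22 + 1 = 23 and 35 + 1 = 36. Only the origin differs.

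**The case against.** The case for leaving the text alone is that neither defect should change much.

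**On the target day.** It is used only when several values qualify, and one PK sample is planned per visit. A patient sampled on Day 29 is normally dosed at the same visit, which restarts the count. A second valid sample therefore needs a withheld or delayed dose together with an unscheduled draw, such as those planned at treatment discontinuation (Protocol 10.3.4) or for a cutaneous allergic event (Protocol 10.6.2.1). SAP 2.5.4 also has a general rule that prefers the scheduled-visit value within a window. If that rule governs PK, an unscheduled later sample would not displace a scheduled one. The PK-specific rule does not repeat the preference, so this is unsettled. All of this stands, and it limits the effect. It does not make 32 the right number.

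A reader might infer that Q4W troughs are in general picked late and biased low. The documents do not support that, because the target is idle for the planned single samples.

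**On the origin.** SAP 2.1.7 is the definition of the variable, and it names alirocumab. Table 7 can fairly be read as shorthand for it. SAP 2.3.2 shows that the authors had sham placebo in mind, since it leaves those injections out when assigning the as-treated group. That also stands. Still, Table 7 carries no such note, and 2.1.7 itself refers to it for the windows.

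A reader might infer that Week 24 troughs will be lost for most of the Q4W alirocumab group, for example 50 × 0.864 ≈ 43 of 50. That needs Table 7 to be applied against 2.1.7. It also carries over the Phase 2 Cohort 4 proportion below 110 mg/dL (Protocol 4) as this trial's non-adjustment rate, and it assumes that all 50 patients reach Week 24. The plan read as a whole keeps these samples.

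Nor do the documents say that troughs in this trial support the choice of Q4W doses. Protocol 4 bases that choice on Phase 2 results.

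**Conclusion.** Day 32 is wrong as written. The value consistent with the 28-day interval, the Q4W window and the Q2W target is Day 29, a difference of 3 days. This rests on the SAP's own figures and is certain. Its practical effect is confined to the uncommon case of a second valid sample in a Q4W window, where it can favour the later sample. The documents give no half-life, so no size in concentration units is claimed.

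The difference in origin between SAP 2.1.7 and Table 7 is a real inconsistency. It does harm only if Table 7 is programmed without 2.1.7, and that conclusion depends on the inferred injection weeks.

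PK is among the other objectives and is summarised descriptively (SAP 1.2.3 and 2.4.8). No efficacy endpoint or hypothesis test is affected. The correction is minor: nice to have.

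**What to change.** - In the text below SAP Table 7, change Day 15/32 to Day 15/29.
- In the Table 7 header and the selection rule, define Day 1 as the day of the previous injection of alirocumab, with sham placebo injections not counted, to match SAP 2.1.7.

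The cost is two wording corrections in the SAP and the matching lines of the programming specification. No window, dose, endpoint or test changes.

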2.5.5 Unscheduled visits

For all parameters, unscheduled visit measurements may be used to provide a measurement for a time point, a baseline, a last or a worst value, if appropriate according to their definitions. The measurements may also be used to determine abnormal/PCSA.

2.5.6 Pooling of centers for statistical analyses

Not Applicable.

2.5.7 Statistical technical issues

Not Applicable.

3 INTERIM ANALYSIS

The analyses will be conducted in 2 steps. The first analysis will not be conducted before completion of the double-blind treatment period. Since analysis of double-blind primary and key secondary efficacy endpoints will have been concluded at the time of the first step analysis described below, no multiplicity adjustment for multiple analyses is needed (see Section 2.4.4.3), and the overall significance level remains at 0.05 for the study.

- First step analysis: Analysis of the completed double-blind treatment period and first step analysis of the open-label treatment period
 - This analysis will be conducted when all patients have been randomized and have at least all their lipid data up to Week 24 analysis window (double-blind period) collected and validated.
 - The efficacy analyses of the double-blind period will consist in the final analysis of the primary and secondary efficacy endpoints (except those measured during open-label period). Analysis of lipid data collected during the OL period will be descriptive.
 - The safety analyses of the double-blind period will not be fully final at the time of this analysis since the double-blind TEAE period will be truncated at the cut-off date for some patients. The safety analyses of the double-blind and open-label treatment periods will be performed on all safety data collected up to the common cut-off date. The common cut-off date is defined as date of the last patient included completed Week 24 visit.
- Final analysis of the open-label treatment period
 - This analysis will be conducted at the end of the study with the data of the open-label treatment period and will consist in the final analysis of the safety and efficacy measures of the open-label treatment period.

Analyses methods and conventions described in the other sections of this SAP will be applied for all analyses as applicable. The following additional rules will apply for analyses performed at first analysis:

- Any lipid assessments within analysis windows up to Week 24 will be taken into account (may include few unscheduled lipid data soon after the cut-off date).
- Open-label period: Patients without end of treatment visit performed at the time of the cutoff date will be considered as ongoing and exposed up to the cut-off date. Therefore:
 - Patients who did not complete treatment period nor prematurely discontinued the study treatment at cut-off date will be analyzed as "ongoing" in the disposition summary.
 - Their open-label TEAE period, open-label treatment period and open-label on-study observation period will end at the cut-off date.
 - Their treatment duration for the open-label period will be derived by considering date of cut-off as last injection date.

- Open-label period: Analyses of number of injections, mean injection frequency, percentage of days with under/above-planned dosing and compliance will be performed up to the last injection reported in the e-CRF up to the cut-off date.
- Double-blind period and open-label period: AEs occurring, worsening or becoming serious after the cut-off date will not be included in the analyses. However, any available outcome before database lock, regardless of timing in relation to the cut-off date, of an adverse event starting prior to the cut-off date will be taken into account. Medications, treatment discontinuations/completions and deaths occurring after the cut-off date will not be included in the analyses.
- Open-label period: Post-treatment period and post-study period are not applicable for ongoing patients. Analyses of post-treatment AEs, post-study deaths and post-treatment medications will be performed for patients who either completed or prematurely discontinued the treatment before or at the cut-off date.
- Analysis of status at last study contact will be provided for patients who prematurely discontinued the study treatment before or at the cut-off date.

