2.4.3.1 Extent of investigational medicinal product exposure

Double-blind period

• Q2W dosing regimen cohort

The exposure during the double-blind period will be assessed using descriptive statistics for:

- The total number of double-blind IMP administrations by patient.
- Duration of IMP exposure in weeks defined as (last dose of double-blind IMP injection date first dose of double-blind IMP injection date + 14 days)/7, regardless of unplanned intermittent discontinuations (see Section 2.5.3 for calculation in case of missing or incomplete data).
- Q4W dosing regimen cohort

The exposure during the double-blind period will be assessed using descriptive statistics for:

- The total number of double-blind IMP administrations by patient.
- Duration of IMP exposure in weeks defined as:
 - (last dose of double-blind IMP injection date first dose of double-blind IMP injection date + 28 days)/7, for patients who stopped definitively the IMP before the switch to Q2W regimen (actual or sham) at Week 12, regardless of unplanned intermittent discontinuations (see Section 2.5.3 for calculation in case of missing or incomplete data).
 - (last dose of double-blind IMP injection date first dose of double-blind IMP injection date + 14 days)/7, otherwise, regardless of unplanned intermittent discontinuations (see Section 2.5.3 for calculation in case of missing or incomplete data).

Non-integer values will be rounded to one decimal place.

All quantitative parameters above will be summarized using number, mean, SD, median, minimum and maximum. In addition, the durations of treatment exposure will be summarized according to the following categories: ≥ 1 day and <4 weeks, ≥ 4 weeks and <8 weeks, ≥ 8 weeks and <12 weeks, ≥ 12 weeks and <16 weeks, ≥ 16 weeks and <22 weeks, ≥ 22 weeks.

OL period

• Q2W dosing regimen cohort

The duration of IMP exposure (in weeks) during the OL period will be defined as (last dose of open-label IMP injection date – first dose of open-label IMP injection date + 14 days)/7, regardless of unplanned intermittent discontinuations.

• Q4W dosing regimen cohort

The duration of IMP exposure (in weeks) during the OL period will be defined as:

- (last dose of open-label IMP injection date first dose of open-label IMP injection date + 28 days)/7, for patients still under Q4W regimen at the end of the open-label treatment period, regardless of unplanned intermittent discontinuations.

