- (last dose of open-label IMP injection date first dose of open-label IMP injection date + 14 days)/7, otherwise, regardless of unplanned intermittent discontinuations.

Duration of IMP exposure will be summarized using number, mean, SD, median, minimum and maximum and according to the following categories: ≥ 1 day and ≤ 24 weeks, ≥ 24 weeks and ≤ 52 weeks, ≥ 52 weeks and ≤ 78 weeks, ≥ 78 weeks.

Combined period (double-blind and OL periods)

In each dosing regimen cohort, study treatment exposure variables combining double-blind and open-label periods are listed below for all patients who received alirocumab in the double-blind period and entered in the OL period:

- Combined duration of alirocumab exposure in weeks, regardless of unplanned intermittent discontinuations.
- The following categories will be used for treatment exposure intervals: ≥ 1 day and <24 weeks, ≥ 24 weeks and <52 weeks, ≥ 52 weeks and <78 weeks, ≥ 78 weeks and <102 weeks, ≥ 102 weeks.

Titration/dose-adjustment

For the double-blind period, the number and percentage of patients with an up-titration/doseadjustment in the alirocumab group during the double-blind period will be described for each dosing regimen cohort.

- In the Q2W dosing regimen cohort, patients with an up-titration are defined as up-titrated patients according to IVRS/IWRS Week 12 transaction with at least 1 injection of alirocumab 75 mg Q2W for patients with baseline BW<50 kg and 150 mg Q2W for patients with baseline BW≥50 kg afterwards.
- In the Q4W dosing regimen cohort, patients with a dose-adjustment are defined as doseadjusted patients according to IVRS/IWRS Week 12 transaction with at least 1 injection of alirocumab 75 mg Q2W for patients with baseline BW<50 kg and 150 mg Q2W for patients with baseline BW≥50 kg afterwards.

For the OL period, the number and percentage of patients with an up-titration/dose-adjustment at Week 32 or thereafter will be described for each dosing regimen cohort, as well as the number and percentage of patients down-titrated at least once. A summary of titration status will be provided by visit. Reasons for up- or down-titration and LDL-C used to up/down-titrate will be summarized, overall and by visit. LDL-C will be summarized quantitatively and with the following categories: <25, ≥ 25 and <50, ≥ 50 and <110, ≥ 110 and <130, ≥ 130 mg/dL.

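### At the first-step analysis, the cut-off date stands in for the last injection and 14 or 28 days are still added, so ongoing patients' open-label exposure runs past the cut-off

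*SAP*

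**What the plan says.** SAP 2.4.3.1 defines open-label exposure in weeks.

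- Q2W cohort: last injection date minus "first dose of open-label IMP injection date + 14 days)/7, regardless of unplanned intermittent discontinuations".
- Q4W cohort, patients still on Q4W: last injection date minus "first dose of open-label IMP injection date + 28 days)/7, for patients still under Q4W regimen at the end of the open-label treatment period".
- Q4W cohort, all others: last injection date minus "first dose of open-label IMP injection date + 14 days)/7, otherwise, regardless of unplanned intermittent discontinuations".

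SAP Section 3 carries these definitions into the first-step analysis: "Analyses methods and conventions described in the other sections of this SAP will be applied for all analyses as applicable". It then adds rules for that analysis. Patients with no end-of-treatment visit by the cut-off "will be considered as ongoing and exposed up to the cut-off date". Two consequences are drawn from this:

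- For exposure, the rule is: "Their treatment duration for the open-label period will be derived by considering date of cut-off as last injection date".
- For the observation periods, it is: "Their open-label TEAE period, open-label treatment period and open-label on-study observation period will end at the cut-off date".

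The cut-off is the date on which the last included patient completes the Week 24 visit.

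**The concern.** The 14 or 28 days in 2.4.3.1 represent the dosing interval covered by a real last injection. Section 3 puts the cut-off date in that slot, although the cut-off is not an injection date. The formula then credits a dosing interval that lies after the data cut. The stated aim is exposure up to the cut-off, and the rule as written does not deliver it.

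Protocol 6.3 allows the first analysis to be used for regulatory consultation, so the open-label exposure table may be read outside the sponsor. Its durations would be too long, and some patients would move up across the 24-, 52- and 78-week category limits. The addition is largest for patients still on Q4W. Their cohort enrolled second and so has the shorter true follow-up.

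**Working it through.** The plan states no figure to reproduce, so the check is date arithmetic on the SAP's own formula. Let A be the addition: 14 days, or 28 days for Q4W-cohort patients still on Q4W.

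**What the addition represents.** Assume a full 80-week open-label period, with the last real injection at open-label week 78 (Q2W) or week 76 (Q4W).

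- Q2W: (546 + 14)/7 = 80.0 weeks.
- Q4W: (532 + 28)/7 = 80.0 weeks.

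With real injection dates the formula returns the planned duration, so the addition is the interval covered by the last dose.

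**First-step rule, read literally.** Duration = (cut-off − first + A)/7.

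| Weeks from first open-label injection to cut-off | A = 14 | A = 28 |
|---|---|---|
| 20 | 22.0 | 24.0 |
| 22 | 24.0 | 26.0 |
| 50 | 52.0 | 54.0 |
| 76 | 78.0 | 80.0 |

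The excess over time to the cut-off is a constant 2 or 4 weeks. If the cut-off day itself counts as exposed, it is 14 − 1 = 13 days or 28 − 1 = 27 days. The second, third and fourth rows show patients reaching or passing the 24-, 52- and 78-week limits.

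**Consistency with the other periods.** In SAP 2.1.4 the open-label treatment period normally ends 21 or 35 days after the last injection and the TEAE period 70 days after it. Exposure (14 or 28 days) therefore normally fits inside both. At the first step both periods stop at the cut-off while literal exposure continues beyond it, so an ongoing patient's exposure is longer than the treatment period that contains it.

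**Against the ordinary formula with real dates.** If the last real injection was g days before the cut-off, the ordinary duration is (last − first + A)/7. The literal first-step duration exceeds it by exactly g days. With on-schedule dosing, g is 0 to 13 (Q2W) or 0 to 27 (Q4W).

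**Total.** With a patients ongoing on Q2W dosing and b still on Q4W, the excess over exposure to the cut-off (that day counted) is 13a + 27b days. The documents give neither number, so these are illustrations:

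- All 150 ongoing, no Q4W patient moved to Q2W: (75 × 13 + 75 × 27)/365.25 = 3000/365.25 = 8.2 patient-years. Counting 14 and 28 days gives 3150/365.25 = 8.6.
- 64 per cohort (half of the 128 left after the planned 15% discontinuation), none moved: (64 × 13 + 64 × 27)/365.25 = 2560/365.25 = 7.0.
- Only the Q4W cohort ongoing, all 75 still on Q4W: 75 × 27/365.25 = 5.5.
- Only the Q4W cohort ongoing, all 75 moved to Q2W: 75 × 13/365.25 = 2.7.

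**The case against.** The duration rule sits under the statement that ongoing patients are exposed up to the cut-off, and other sections' conventions apply only as applicable. A programmer could reasonably stop the duration at the cut-off. That is probably the intent, but the text does not say so. Someone who follows 2.4.3.1 and Section 3 as written will add the days.

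The ordinary formula with real dates can also run past the cut-off, so not all of the 2 or 4 weeks comes from the substitution. This stands. The substitution itself adds only the gap between the last real injection and the cut-off.

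Three stronger readings are tempting, and the documents do not support them.

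- **A Q4W patient starting open label on the cut-off day is credited with 4.0 weeks because of Section 3.** The ordinary formula gives the same (0 + 28)/7 = 4.0 weeks for a single real injection that day. The example reflects the general definition of exposure, not the substitution.
- **The table will be inflated by about 8 patient-years.** That needs all 150 patients ongoing and no Q4W patient moved to Q2W. The plan assumes 15% discontinuation, open-label adjustment from Q4W to Q2W is possible from Week 32, and the Q2W cohort enrolled first, so some of it may have finished.
- **Safety rates are diluted.** In SAP 2.4.5.1 the open-label event rate uses time to first event or the length of the TEAE period, and that period ends at the cut-off. Injection counts, injection frequency and compliance use injections recorded up to the cut-off.

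**Conclusion.** The point holds as a minor error in the rule as written. For each patient ongoing at the first step, literal application carries open-label exposure 14 days past the cut-off, or 28 days for Q4W-cohort patients still on Q4W at that date. The per-patient size follows from the formula alone. The smaller excess against the ordinary formula assumes on-schedule dosing, and any total rests on counts that the documents do not state.

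The effect is confined to descriptive open-label durations and categories at the first step. Combined double-blind and open-label exposure is affected only if it is built from those durations, since SAP 2.4.3.1 gives no formula for it. Efficacy results are untouched, and the final analysis is run at the end of the study, when the rule for ongoing patients no longer applies.

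**What to change.** Replace the duration rule in SAP Section 3 with one sentence: for patients ongoing at the first-step analysis, open-label duration in weeks is (cut-off date − first open-label injection date + 1)/7, without the 14- or 28-day extension.

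An alternative is the actual last injection plus 14 or 28 days, truncated at the cut-off. The two agree when dosing is on schedule; for a patient whose injection is overdue at the cut-off, the alternative gives the shorter duration. Whichever is chosen should also feed the combined exposure summary.

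The cost is one SAP sentence and slightly smaller interim exposure figures. No new data are needed.
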